## 3.5 Interventions:

3.5.1 Control group: sponge restraint band, restraint method: adjust the fixed wrist band according to the wrist diameter of the patient's hand (foot), and then circle the fixed band around the wristband, one end of the puncture hole without tying, and the two ends of the fixed band are fixed on both sides of the bed as needed.

3.5.2 Experimental group: new restraint appliance, which is an adjustable protective restraint device (patent No. ZL202020155913.1), including upper bracket 1, upper bracket 2, lower bracket 2 and gloves; the multiple fixed supports are provided with air holes and breathable cotton to increase air permeability and comfort. Place the patient's elbow with the lower fixed bracket one and two, and then connect the upper fixed bracket one and the upper and lower fixed bracket two, and adjust the tightness, and the other to form a removable and rotating connection in a certain angle range to adjust the movement angle of the patient's elbow joint; set the patient's hand with the palm of the glove. The device was commissioned by Anshan Deyi Da Medical Device Technology Co., LTD. (Business license registration number: 912103003966197061, class I medical device production record No.: Liaoan Food and Drug Device Production Preparation 20200011).

## 3.6, Outcome measures

.13.6 Outcome decision time

This study starts with the use of the protective restraint tool after surgery until the removal of the endotracheal tube..23.6 Main outcome measures

I Adverse event rate of nursing care:

Unplanned extubation rate: unplanned extubation includes a self-extubation without the consent of medical staff; b. Pipeline slip caused by various reasons; c. Extubation needs to be performed in advance due to catheter quality problems and catheter blockage. Unplanned extubation rate = number of unplanned extubation cases in the same period / total number of ICU inpatients in the statistical period 100%. .73 Data collection

Data were collected by on-site assessment and medical record review. General demographic data including age, gender, education, marital status, occupation, smoking, alcohol consumption, health insurance type, surgical mode, admission diagnosis, history of underlying diseases, were collected by the investigator by medical record review. The incidence of nursing adverse events, duration of restraint period, cumulative dose of sedation used, length of ICU stay, and total cost of ICU treatment were collected by the investigator through the electronic medical system and integrated nursing information platform before pre-transfer to the ICU. Anxiety, depression and comfort were assessed by the responsible nurse within 24h after the patient woke from anesthesia and on the day the patient was pre-transferred out of the ICU.

.83 Quality control

.8.13 The hospital has established a unified and standardized restraint process, and will regularly regular restraint and skin care training for nurses.

.23.8 Each class has a responsible leader, who will check the skin assessment and the rigor of nursing records, and ensure the quality of nursing records.

3.8.3 Double verification during data collection and entry.

.93 Statistical analysis

.0 Statistical analysis by SPSS 25 software, frequency and percentage for count data, chi-square test or Fisher test for between-group comparison, mean  $\pm$  standard deviation for normal distribution data, t-test for groups, non-normal distribution data, and non-parametric test for between-group comparison. A P <0.05 was considered as a statistically significant difference.

4.1 The subjects analyzed in this study are all vulnerable groups after cardiac surgery. For subjects, the data obtained in this study are only used for research, and they are not publicly available outside the scope permitted by relevant laws and / or regulations.

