#### 3. Study design and method:

3.1 This study used random number table to divide the subjects into control and experimental groups.

3.2 The research period of the whole project starts from the date of ethical passage and ends in 2024.

3.3 Inclusion criteria: ① elective surgery patients, age 18; ② preoperative awareness and no communication impairment; ③ open heart surgery under intravenous or inhalation general anesthesia; ④ ICU\_During the treatment, endotracheal intubation existed; before ⑤ restraint, there was no joint dysfunction, edema, skin damage, etc. at the proposed restraint site, and the peripheral circulation was good;
⑥ gave informed consent to participate in this study. Exclusion criteria: ① had a history of mental illness; ② had bleeding tendency or skin disease; voluntary abandonment of treatment or death in ③.

3.4 Sampling strategy and grouping: This study used the convenient sampling method to select the research subjects, and then the included subjects were randomly divided into control group and experimental group according to the coin throwing method. The control group used the restraint appliance as the sponge restraint belt, and the experimental group used the restraint appliance as the new restraint appliance.

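### The main outcome formula divides unplanned extubations by all ICU inpatients in a period, so it does not give the risk in each randomised arm

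*Protocol*

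**What the plan says.** Section 3.6.2 of the protocol (Main outcome measures) opens with "Adverse event rate of nursing care" and defines one component under it, unplanned extubation. It gives one formula for the rate: "number of unplanned extubation cases in the same period / total number of ICU inpatients in the statistical period", expressed as a percentage.

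Other parts of the protocol describe a different population, time window and comparison:

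- Section 3.3 limits entry to consenting elective open heart surgery patients, and for their ICU stay requires "During the treatment, endotracheal intubation existed".
- Section 3.4 takes a convenience sample, after which "the included subjects were randomly divided into control group and experimental group".
- Section 3.6.1 sets the time frame: "This study starts with the use of the protective restraint tool after surgery until the removal of the endotracheal tube".
- Section 3.9 plans, for count data, "chi-square test or Fisher test for between-group comparison".
- Item 4.1 adds: "The subjects analyzed in this study are all vulnerable groups after cardiac surgery".

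No section restates the extubation rate with a denominator for each arm.

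**The concern.** A two-arm randomised trial estimates the risk of the event among patients allocated to each arm. The written denominator counts ICU inpatients whether or not they were intubated, restrained, eligible, consenting or randomised, and it also counts the patients of the other arm. It is tied to a reporting period, whereas 3.6.1 follows each patient from start of restraint to tube removal.

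No other outcome is defined under the main outcome heading, so the trial's headline figure depends on this formula. Section 3.7 takes adverse event data from the electronic medical system and the nursing information platform, so an ICU-wide total could plausibly be used where an arm count is needed. At stake are the reported absolute risks and risk difference and, if the arms differ in size, the risk ratio.

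**Working it through.** **There is no figure of the plan's own to reproduce.** The protocol gives no expected rate, effect size or ICU census, and the group size in the sample size section is not legible. What follows is algebra, then illustrations on declared assumptions.

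**Algebra.** Let an arm have n patients and e events, and let M be all ICU inpatients in the period.

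- Risk in the arm: e/n.
- Formula with only the numerator split by arm: e/M = (e/n) × (n/M).
- Difference between equal arms: true difference × (n/M).
- Ratio of the two arms: (e1/M)/(e2/M) = e1/e2 = true risk ratio × (n1/n2).

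So absolute figures shrink by n/M. The ratio is right only when n1 = n2. If the numerator is not split either, there is a single ICU-wide rate and nothing to compare.

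**1. Dilution.** Assumed: n = 50 per arm, 10 v 2 events, M from 200 to 1000.

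| Denominator | Arm with 10 events | Arm with 2 events | Difference (points) |
|---|---|---|---|
| 50 (own arm) | 20% | 4% | 16 |
| 200 | 5.0% | 1.0% | 4.0 |
| 500 | 2.0% | 0.4% | 1.6 |
| 1000 | 1.0% | 0.2% | 0.8 |

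The factor n/M runs from 50/200 = 0.25 to 50/1000 = 0.05, a 4- to 20-fold dilution.

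**2. Unequal arms.** Assumed: arms of 60 and 40 with 6 and 4 events. True risks are 6/60 = 4/40 = 10%, ratio 1.0. With M = 1000 the formula gives 0.6% v 0.4%, ratio 1.5 = 60/40.

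Section 3.4 allocates by coin throwing. For 100 patients and a simple fair coin (binomial, 100 tosses, probability 0.5):

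- exactly 50:50 has probability 0.080;
- 55:45 or worse has probability 0.368, with a bias factor of at least 55/45 = 1.22;
- 60:40 or worse has probability 0.057, with a factor of at least 1.5.

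These probabilities apply only if the coin is used. Section 3.1 names a random number table, and the sample size section implies equal groups.

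**3. The test.** Section 3.9 does not say that the ICU census enters the chi-square or Fisher test. If it did, two-sided Fisher P-values would move as follows (first column: 50 per arm; other columns: M in each row of the table):

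| Events | n = 50 | M = 200 | M = 500 | M = 1000 |
|---|---|---|---|---|
| 6 v 0 | 0.027 | 0.030 | 0.031 | 0.031 |
| 8 v 1 | 0.031 | 0.037 | 0.038 | 0.039 |
| 10 v 2 | 0.028 | 0.036 | 0.038 | 0.038 |
| 15 v 6 | 0.048 | 0.071 | 0.075 | 0.077 |
| 20 v 10 | 0.049 | 0.086 | 0.094 | 0.096 |

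The shift is small when events are uncommon. It crosses 0.05 only in the last two rows, where one arm has a risk of 30% (15/50) or 40% (20/50).

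**The case against.** The strongest reply is that the rest of the plan already implies the right table. A chi-square or Fisher test between groups needs patients with and without the event in each group, item 4.1 describes the analysed subjects as cardiac surgery patients, and 3.6.1 sets a window for each patient. No section tells the analyst to put the ICU census into the test, and none describes splitting the numerator but not the denominator. The text reads as a translation, so loose wording is more likely than an intention to analyse the trial this way. The period in the formula might even be meant as the 3.6.1 window.

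It can also be said that every magnitude is assumed, that equal arms preserve the ratio, that the examples crossing 0.05 need risks of 30% to 40% which the protocol does not support, and that the 60:40 example would not give a false positive (Fisher P about 0.75 at a census of 200 to 1000). Section numbering is damaged in this part of the text, so further main outcomes may have been lost. Finally, dividing by all randomised patients settles an analysis set that a SAP might otherwise define.

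Much of this stands as a limit on size: the distortion cannot be derived from the protocol, and harm to the P-value is conditional and usually small. It does not remove the defect. Likely intent does not correct a written rule, and a SAP that followed this formula would inherit the error, while one that did not would contradict the protocol. Dividing by patients randomised to the arm is the standard unbiased denominator for a two-arm trial.

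**Conclusion.** The concern holds, and the formula must be corrected before analysis. The stated denominator contradicts the trial population (3.3, 3.4), the patient-level window (3.6.1) and the planned between-group test (3.9). This conclusion needs no assumed number.

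Followed as written, the formula gives either no arm contrast or arm risks scaled by arm size over ICU census. Under the assumed 50 per arm and census of 200 to 1000, absolute risks and the risk difference come out 4 to 20 times too small. The risk ratio is unaffected with equal arms and is multiplied by the ratio of arm sizes otherwise. The effect on P-values arises only if the same denominator is carried into the test.

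**What to change.** In 3.6.2, replace the formula with: number of patients randomised to the arm who had an unplanned extubation between start of restraint and removal of the endotracheal tube, divided by the number of patients randomised to that arm, × 100%.

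In 3.9, add that these counts of patients with and without the event in each arm form the table for the chi-square or Fisher test.

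The cost is one sentence and one clause. No new data are needed: the events are already collected as nursing adverse events and the denominators come from the allocation list. The one loss is that the trial rate will no longer be directly comparable with the unit's quality indicator.

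### Section 3.9 names only unadjusted two-group tests, so the continuous outcomes give up precision that baseline data already collected under 3.7 could supply

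*Protocol*

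**What the plan says.** Section 3.9 of the protocol chooses the test by type of data. Counts get "chi-square test or Fisher test for between-group comparison". Continuous data get "t-test for groups, non-normal distribution data, and non-parametric test for between-group comparison". The threshold is "A P <0.05 was considered as a statistically significant difference". No regression or other covariate-adjusted analysis is named, and the section does not refer to a later plan. Nor does it say that these are the only analyses.

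Section 3.7 lists the baseline data: "General demographic data including age, gender, education, marital status", and later in the same list "surgical mode, admission diagnosis, history of underlying diseases". It also lists the continuous outcomes: duration of restraint, cumulative sedation dose, length of ICU stay, ICU cost, and anxiety, depression and comfort. The only measure defined under the main outcomes in 3.6 is binary, the unplanned extubation rate.

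On allocation, 3.1 says "This study used random number table to divide the subjects into control and experimental groups", while 3.4 says patients were "randomly divided into control group and experimental group according to the coin throwing method". Neither mentions stratification or blocking.

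**The concern.** Age, type of operation and diagnosis plausibly explain part of the variation in ICU stay, ventilation-linked restraint time, sedation and cost. An unadjusted comparison leaves that variation in the error term. If the share is material, the intervals for the device effect are wider than they need be, and a real difference is more easily missed, although the data to narrow them are in hand. As 3.9 reads, an analyst following it would not use them.

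**Working it through.** **Inputs from the protocol.** The tests and the 0.05 level (3.9), the baseline items and continuous outcomes (3.7), and the binary main outcome (3.6). Two-sided testing is assumed, as 3.9 does not state it. The protocol gives no power, effect size, standard deviation, event rate or explained variance, so it has no figure of its own to reproduce. Section 4 prints 5 per group in a visibly garbled sentence, so the planned number is unknown. The sizes below are illustrative.

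**Assumption.** The covariates explain a share R² of the within-arm outcome variance, from 0.1 to 0.4.

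**Step 1: gain before any cost.** Adjustment multiplies the standard error by √(1 − R²). At R² = 0.1 this is √0.9 = 0.949, and at R² = 0.4 it is √0.6 = 0.775.

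**Step 2: cost of estimating the covariates.** With N patients in total and k covariates, the variance is inflated on average by (N − 3)/(N − k − 3). For k = 3:
- 25 per arm: 47/44 = 1.068
- 50 per arm: 97/94 = 1.032
- 100 per arm: 197/194 = 1.015
- 5 per arm: 7/4 = 1.75

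Adjustment pays only if R² exceeds 1 − 1/inflation: 0.064, 0.031, 0.015 and 0.43 respectively.

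**Step 3: power.** Take the effect with 80% power in the unadjusted t-test, divide its non-centrality by √[(1 − R²) × inflation], and read power from the non-central t with N − 2 − k degrees of freedom. At 25 per arm the non-centrality is 2.859. At R² = 0.1 the divisor is √(0.9 × 1.068) = 0.980, giving 2.859/0.980 = 2.917 on 45 degrees of freedom and 81.4% power.

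| Per arm | k | R² = 0.1 | 0.2 | 0.3 | 0.4 |
|---|---|---|---|---|---|
| 25 | 3 | 81.4% | 85.7% | 89.9% | 93.8% |
| 50 | 3 | 82.8% | 86.9% | 90.9% | 94.5% |
| 100 | 3 | 83.4% | 87.5% | 91.4% | 94.8% |
| 5 | 3 | 53.8% | 58.6% | 64.1% | 70.6% |
| 5 | 1 | 76.4% | 81.0% | 85.8% | 90.4% |

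Simulation (12,000 trials per setting) agrees at 25 per arm: 81.2% to 93.9%. At 5 per arm with three covariates the average-inflation formula is rough, and simulation gives 59% to 74%. Either way power falls below 80%.

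**Step 4: is the unadjusted test valid?** In 15,000 simulated trials per setting, with simple randomisation of 10, 100 or 200 patients and a covariate with R² of 0.1 or 0.3 left to chance, the unadjusted t-test rejected a true null in 4.8% to 5.2% of trials. It keeps its level.

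**Step 5: the main outcome.** For a binary event, a covariate with an odds ratio of 2 per standard deviation explains 1.1%, 2.6% and 4.5% of the variance at assumed event rates of 2%, 5% and 10%. The gain is close to nil.

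**The case against.** The strongest reply is that nothing in 3.9 is wrong. The tests are standard and valid, covariates are commonly specified in a statistical analysis plan that is not shown here, and 3.9 does not rule adjustment out. All of that stands, and it makes this a choice of a less efficient method and not an error. It does not remove the point: 3.9 goes as far as fixing a test for each data type, and followed as written the analysis is unadjusted.

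A reader might infer more: that without stratification a chance difference in case mix is left uncorrected and biases the device effect. The documents do not support that. Under randomisation such differences are already allowed for in the standard error and p-value, as Step 4 shows. What remains is narrower. Among simulated null trials of 100 patients in which a factor present in 40% happens to differ by at least 15 percentage points, the unadjusted test rejects 9%, 11% and 14% of the time at R² of 0.1, 0.2 and 0.3. The other trials balance this out. It is a reason to choose covariates beforehand, not evidence of bias. Nor can coin tossing be taken as the settled method, since 3.1 names a random number table; that conflict is a separate matter.

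Two further objections stand. The gain does not reach the main outcome, and its size rests on an R² that the protocol does not document.

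**Conclusion.** The point holds as a modest matter of efficiency for the continuous outcomes. Under the assumed R² of 0.1 to 0.4, power rises from 80% to about 81% to 94% with three covariates at 25 per arm, and to about 83% to 95% at 100 per arm. At the low end of R² in a small trial the gain is about one percentage point. If the sample really were 5 per arm, three covariates would do harm, and one would help only if R² exceeded about 0.14 (1 − 6/7). That the covariates are collected and no adjusted analysis is named is certain from the text; the size of the gain is not. It would be wrong to conclude that the planned tests are invalid, that imbalance biases the result, or that the extubation comparison needs adjustment.

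**What to change.** In 3.9, before any outcome data are seen:
- For restraint duration, sedation dose, ICU stay, cost and the three scores, specify a linear regression on arm with a small named set of baseline covariates, for example age and surgical mode. Use one covariate or none if the final sample is very small.
- Use a log scale for skewed durations and costs, and say that the result is then a ratio. State how zero values, if any, are handled.
- Report the adjusted difference (or ratio) with its 95% confidence interval, and keep the unadjusted tests as a sensitivity analysis.
- Use only covariates fixed before restraint starts. The first anxiety, depression and comfort assessment falls within 24 hours after waking from anaesthesia, while 3.6 counts the study from the start of restraint after surgery, so that score may already reflect the device.
- Leave unplanned extubation with the unadjusted chi-square or Fisher test.

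The cost is a few sentences and a little more analysis in the SPSS package already named; no new data are needed. The one real risk is loss of precision from too many covariates in a very small sample, so the number should be set once the sample size in section 4 has been stated legibly.

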#### 4, and the sample size calculation

The test group and the control group were selected separately 5 For example, patients.

All records concerning the identity of the subject are kept confidential and are not publicly available beyond the extent permitted by the relevant laws and / or regulations.

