## 2, and the study purpose

According to the individual characteristics of ICU patients, combined with the needs of patients, the innovative production of a new restraint appliance and study the effectiveness and safety of the new restraint appliance, to provide clinical reference and theoretical basis for the standardization of postoperative patient restraint.

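### Does a printed size of 5 patients per arm make the P<0.05 comparison of unplanned extubation unworkable?

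*Protocol*

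**What the plan says.** Section 4 of the Protocol gives the size of the two groups as "The test group and the control group were selected separately 5 For example, patients". It states no expected event rate, effect, power or dropout.

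The main outcome under section 3.6 is the adverse event rate of nursing care. The component spelled out is unplanned extubation ("Unplanned extubation rate: unplanned extubation includes a self-extubation without the consent of medical staff", plus tube slippage and early removal for catheter faults). The rate is defined as "number of unplanned extubation cases in the same period / total number of ICU inpatients in the statistical period".

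The statistical analysis paragraph, which appears under the same heading, covers all count data with "chi-square test or Fisher test for between-group comparison" and adds "A P <0.05 was considered as a statistically significant difference". It does not say when each test applies, whether chi-square is continuity-corrected, or whether tests are two-sided.

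The aim in section 2 is to "study the effectiveness and safety of the new restraint appliance".

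**The concern.** Taken at face value, 10 patients in total are to be compared on a binary safety event by a significance test. Almost every possible result would then be non-significant, and a reader might take that as showing the new device to be as safe as the sponge belt. In a few tables the two permitted tests would also disagree, so a significant finding could depend on which test was run. Since the patients are postoperative and intubated, enrolling them in a comparison that cannot inform its own aim would be a serious matter. The section also carries the title of a calculation without containing one.

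**Working it through.** **Inputs.** From the Protocol: 5 per arm as printed (section 4), 1:1 allocation implied by one figure for both groups, P<0.05, and chi-square or Fisher for count data. Assumed: two-sided testing, each arm's own patients as the denominator, and all event rates, since the Protocol gives none. There is no calculated sample size to reproduce.

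**Step 1: rejection sets at 5 per arm.** With a and b events in the two arms, the probability of a table given its margins is C(5,a)·C(5,b)/C(10,a+b). In these tables the opposite tail is the mirror image, so the two-sided P is twice that value.

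- 5/5 vs 0/5: 2 × 1/252 = 0.0079
- 4/5 vs 0/5: 2 × 5/210 = 0.0476; 5/5 vs 1/5 is the same by symmetry
- 3/5 vs 0/5: 2 × 10/120 = 0.167; 5/5 vs 2/5 is the same by symmetry

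Every table other than the first three and their mirror images has a Fisher P of at least 0.167.

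Uncorrected chi-square for 3/5 vs 0/5 is 10 × (3·5 − 2·0)² / (5·5·3·7) = 2250/525 = 4.29, P = 0.038. It therefore rejects at 3/5 vs 0/5 and 5/5 vs 2/5 in addition to the Fisher set. With Yates correction only 5/5 vs 0/5 rejects (P = 0.0114), because 4/5 vs 0/5 gives 0.0528. The smallest expected cell count is at most 2.5 in every table. The maximum type I error is 0.0215 for Fisher, 0.0618 for uncorrected chi-square and 0.002 with Yates correction.

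**Step 2: exact power at 5 per arm.** Power is the sum, over rejecting tables, of the product of the two binomial probabilities.

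| Assumed rates | Fisher | Uncorrected chi-square |
|---|---|---|
| 10% vs 2% | 0.04% | 0.8% |
| 20% vs 5% | 0.5% | 4.5% |
| 30% vs 5% | 2.4% | 12.7% |
| 50% vs 10% | 12.1% | 30.8% |

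At 50% vs 5% Fisher power is 15%. With 0/5 events the exact 95% upper limit is 1 − 0.025^(1/5) = 52%.

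**Step 3: can the digit be trusted?** The sentence is not grammatical: a connecting phrase stands where a number and unit would be expected. Nearby numerals are also disturbed. Subsection numbers under 3.6 print with their digits out of order, a stray decimal fragment opens the statistical analysis paragraph although the software version follows later in the line, and the age criterion has lost its comparison sign. An incomplete number is a realistic reading.

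**Step 4: what if a digit is missing?** As an illustration, take a second digit lost after the 5, giving 50 to 59 per arm. Exact Fisher power is then:

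| Assumed rates | n=50 | n=55 | n=59 |
|---|---|---|---|
| 10% vs 2% | 19% | 23% | 27% |
| 20% vs 5% | 51% | 57% | 62% |
| 25% vs 5% | 75% | 80% | 84% |
| 30% vs 5% | 90% | 93% | 95% |

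At this size the trial may be poorly or well powered depending wholly on rates the Protocol does not supply. Against zero events in the other arm, Fisher needs 6 events and uncorrected chi-square 4, so the tests still differ at the margin.

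**The case for a change.** The strongest case for a change does not need the digit to be right. Section 4 claims to be a calculation and shows no basis for any number, so this is not detail left to an analysis plan. The choice between tests matters at other sizes too: from 15 to 95 per arm, uncorrected chi-square rejects at 4 events vs 0, while Fisher needs 5 (at 15) or 6 (at 25 and above). At 10% vs 2%, Fisher power is still only 55% at 95 per arm. The remedy would be a matter of wording: call the trial a pilot, name one exact test, and report counts with an exact interval.

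Part of this stands. The size has no stated basis, and the two tests can disagree at the margin. The all-inpatient denominator in section 3.6 is no answer to it either, since a between-group test needs each arm's own patients.

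The rest does not carry. The 55% figure rests on one assumed pair; at 25% vs 5% the same 95 per arm gives 97%. The test list is a standard phrase for all count data, and the rule for choosing is commonly left to the analysis plan. With few events a competent analyst goes to Fisher without being told. Relabelling the trial a pilot and withdrawing its inference would be a large step to take on one doubtful character.

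**Conclusion.** No change to the plan follows. The figures for 5 per arm are right: three Fisher-rejecting tables and their mirror images, two further ones under uncorrected chi-square, and Fisher power from 0.04% to 15% over the assumed rates. They hold only if 5 is the whole number, and the state of the text makes that doubtful.

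Even on the literal reading, the Protocol is not contradicted by its own figures. It states no target power, effect or event rate, so its size cannot fall short of one, and low power by itself is not an error in the plan. It states an aim to study effectiveness and safety; it contains no rule that turns P>0.05 into equal safety. The open choice between chi-square and Fisher is a gap that analysts fill sensibly.

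What is left is a question to the sponsor: what number per arm is meant, and which extubation rates and power does it rest on? If the answer were indeed 5, the results should be read descriptively, as counts and a risk difference with an exact 95% interval and Fisher as the test, and non-significance should not be taken as reassurance. This conclusion assumes two-sided testing and per-arm denominators.
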